#### **Safety concerns related to study procedures:**

***EGG with satiety testing:*** EGG recording involves placement of EGG electrodes on the abdominal surface. There may be some soreness in removing the EGG electrodes. Otherwise, there are no immediate risks to EGG or the consumption of Ensure® during the satiety test.

**Other Risks:** Blood draw may cause discomfort, such as swelling, temporary sensation of pain, or burning and/or a bruise that may develop and last for a few days. Less common risks include a blood clot at the site of puncture or swelling of the vein and surrounding tissues, and possible bleeding from the puncture site.

**Safety issues related to patient privacy:**

It is the investigator's responsibility to conduct the protocol under the current version of Declaration of Helsinki, Good Clinical Practice, and rules of local IRBs. The investigator must ensure that the patient's anonymity be maintained in their data submission to the Data Coordinating Center. Patients will be identified only by an identification code but not by their name, SSN, or hospital medical record number. Investigators will maintain a separate confidential enrollment log which matches identifying codes with the patients' names and addresses (i.e., available only to local clinic staff). All study material will be maintained in strict confidence.

### 5.8 Adherence and retention

Two important goals of this protocol are to optimize adherence to the pharmacological regimen and to maximize the retention of participants in the study. Assessment of adherence to the assigned study medication will provide clinic staff a means to identify participants having problems with adherence. Adherence will be assessed by:

- Counts of capsules in the patient's returned study medication bottles
- Conducting a brief, structured interview, in which the study coordinator will assist the patients to identify problems in taking the study medication and to estimate adherence to the prescribed medicine since their previous visit.

These assessments will guide the consideration of strategies to improve adherence.

### 5.9 Management of concomitant conditions

All other illnesses will be managed in conjunction with the patient's primary care physician according to the protocols described in the Standards of Care for Patients with Idiopathic Gastroparesis (SOP IV) document prepared by the GpCRC Steering Committee.

In the event of major dermatological reactions such as generalized urticaria, bullous rashes, exfoliative dermatitis, or Stevens-Johnson Syndrome, study medication will be discontinued immediately and not restarted. For local skin reactions, study medication may be discontinued if the skin reactions are potentially drug related. If the rashes clear, the study medication may be restarted. If local skin reactions recur with restarting the study medication, study medication should be discontinued. In cases where the study medication has been discontinued, the study medication will be unmasked after the completion of the trial and the participant, investigator, and the primary care provider will be notified in order to prevent future exposures.

### 5.10 Food and Drug Administration

The NORIG trial will be conducted under an Investigational New Drug (IND #102,404) held by the NIDDK. The investigators will complete a Statement of Investigator (FDA Form 1572) per the Code of Federal Regulations before the initiation of the NORIG trial. The safety data required to meet IND regulatory requirements will be collected through adverse event reporting by the clinic investigators and will be provided by the Data Coordinating Center to the NIDDK for transmission to the FDA.

### 5.11 Adverse event reporting

The NORIG trial will monitor and report adverse events to ensure patient safety. There are two separate sets of government regulations that apply to unanticipated or adverse events in research studies: (1) 45 CFR Part 46, Subpart A; the “Common Rule”, shared by 17 Departments and Agencies and (2) 21 CFR 312, the FDA regulation for adverse events. The Common Rule requires written procedures and policies for ensuring reporting of “unanticipated problems” involving risks to participants to IRBs, appropriate institutional officials, and the Department or Agency Head. The FDA regulation requires notification of the FDA and participating investigators of any adverse event associated with the use of a test article that is “both serious and unexpected.” Since the definitions and reporting requirements for unanticipated events differ between the two sets of Federal regulations, the NORIG trial definitions and procedures for adverse events are designed to satisfy both sets of requirements.

#### Definitions

**Adverse event.** An adverse event is any untoward medical occurrence that may present itself during treatment or administration with a pharmaceutical product or clinical procedure and which may or may not have a causal relationship with the treatment. Adverse events include any unanticipated problems involving risks to participants, or breaches of protocol which might entail risk to participants. The term "unanticipated problem" includes both new risks and increased rates of anticipated problems.

**Serious adverse event.** A serious adverse event (SAE) is an adverse event occurring at any time during the study that results in death, life-threatening adverse drug experience, inpatient hospitalization or prolongation of existing hospitalization, a persistent or significant disability or incapacity, or a congenital anomaly or birth defect. Other events may also be considered an SAE if, based on medical judgment, the event jeopardized the patient to the point of requiring medical or surgical intervention to prevent the occurrence of any of the conditions for an SAE listed above.

**Unexpected adverse event.** An unexpected adverse event is any adverse event with specificity or severity that is not consistent with the risk information in the study protocol, current investigator brochure, or current package insert.

**Associated with the use of the drug** means that there is a reasonable possibility that the adverse experience may have been caused by the drug.

Adverse events will be recorded on study data forms whether or not they are thought to be associated with the study or with one of the study drugs. Adverse events may be discovered during regularly scheduled visits or through unscheduled patient contacts between visits.

Summary data on adverse events will be monitored by the DSMB quarterly and at its semi-annual meetings or more frequently, as needed. These summaries will include analyses comparing rates of adverse events by treatment group, by clinic, or in other subgroups requested by the DSMB. Where applicable, signs and symptoms associated with the adverse event will be graded as to severity by the clinical site staff as mild, moderate, or severe using the Common Terminology Criteria for Adverse Events.

After each meeting, the DSMB will issue a written summary of its review of the study data, including adverse events, for transmission to the IRBs at each of the study centers. Analyses or listings of adverse events will not be provided to the IRBs; however, adverse events involving unanticipated problems involving risks to participants, or breaches of protocol which might entail risk to participants must be reported to local IRBs as soon as possible after they are discovered. Each participating center is responsible for ensuring that all local IRB requirements for reporting adverse events are met. A summary of adverse events will be reported to the FDA as part of the IND annual report.

#### **Reporting serious adverse events**

Serious adverse events (SAE) must be reported upon discovery at the clinical center per local IRB guidelines. This may involve completing an SAE form per local IRB guidelines, describing the severity and details of the event. If the serious adverse event is judged by the study physician to be associated with the study drug and unexpected per the package insert and above definitions, the SAE form, together with a memo summarizing the circumstances of the event and the current status of the patient, must be faxed to the Data Coordinating Center and to the NIDDK project officer within one working day of the discovery of the SAE and confirm receipt via email or telephone. The NIDDK project officer will work with the Data Coordinating Center to transmit the SAE form and memo to the DSMB Chairperson and Steering Committee members and all participating center investigators.

The DSMB Chair and NIDDK Project Officer will determine if all DSMB members should be made aware of the event at that time, or it is appropriate to wait until the next DSMB meeting. The DSMB wishes to remain masked, therefore, the SAE report should not unmask the readers.

As described above, if the serious adverse event is judged by the study physician as both unexpected AND associated with the study drug, then the NIDDK project officer will work with the DCC to notify the Steering Committee, all participating center investigators, the DSMB and the FDA no later than 15 days from the discovery of the SAE (no later than 7 days if the SAE is fatal or life threatening). The clinical center investigator may also complete an FDA MedWatch 3500 form.

The DSMB will review all SAE reports, at least quarterly. On a case-by-case basis, the NIDDK program staff, in conjunction with the DSMB chairperson, will determine whether the DSMB should review SAE reports more expeditiously.

The clinical center must submit to the NIDDK project officer and to the Data Coordinating Center a follow-up memo within one month of the SAE (and periodic updates if needed) to report the details of the disposition of the SAE. The NIDDK project officer will work with the Data Coordinating Center to distribute the follow-up memo to the Steering Committee, all participating center investigators and to the DSMB.

#### 5.12 Procedures for unmasking treatment assignment

Treatment assignments are double masked throughout the study until all data collection for the NORIG trial has been completed (i.e., after completion of the 18 weeks of treatment and follow-up for all patients). Every effort will be made to maintain the masking throughout the study except in emergency situations. The code for masked study drug will not be broken without the knowledge of the clinical center's principal investigator. Even if the study drug is interrupted or terminated, as needed, the participant will continue with remaining NORIG follow-up visits as scheduled.

Unmasking of study medication will occur under the following conditions:

- **Severe allergic reaction (Stevens-Johnson Syndrome):** Study medication is stopped indefinitely. The patient, primary care provider (PCP), and the investigator will be unmasked.
- **Pregnancy during the study:** Study medication will be stopped indefinitely, and the coded medication will be unmasked. The patient, PCP, and investigator will be notified of the assigned treatment and the associated risks of teratogenicity.
- **Development of significant arrhythmias:** Study medication is stopped indefinitely. The patient, primary care provider (PCP), and the investigator will be unmasked.
- **Development of persistent electrolyte imbalance:** As described in Section 5.7, if the electrolyte imbalance has not been remedied with oral supplementation as indicated by a serum potassium of <3.0 mEq/L and serum magnesium of less than 1.0 mEq/L, the study drug will be stopped. The patient, primary care provider (PCP), and the investigator will be unmasked.
- **Development of persistent enzyme elevation:** As described in Section 5.7, if alkaline phosphatase, alkaline aminotransferase (ALT), or aspartate aminotransferase (AST) enzyme elevations persist above 3 times the upper limit of normal, the study drug will be stopped. The patient, primary care provider (PCP), and the investigator will be unmasked.

- **Development of thrombocytopenia:** As described in Section 5.7, if thrombocytopenia <100,000 cells per  $\mu\text{L}$  develops, the study drug will be stopped. The patient, primary care provider (PCP), and the investigator will be unmasked.

In unforeseen situations where the clinical center principal investigator considers unmasking is in the best interest of the participant's health and well being, unmasking may be done after notifying the Executive Committee. The Data and Safety Monitoring Board will review all instances of unmasking that occur.

---

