### 3.4 Restarts and dose adjustments due to side effects

A standardized management plan for potential side effects and symptoms is detailed in section 5.7 Safety issues. If a common, non-serious side effect to the study drug develops which is noticeable but tolerable, investigators will follow a standardized management plan as outlined in section 5.7 of the protocol. These side effects include ones commonly seen with TCAs such as constipation, dry mouth, weight gain, bloating, dizziness, insomnia. The management plan for these common, non-serious side effects generally involves patient education about the side effect and adding over the counter therapies. The study drug is continued with dose escalation. If the side effect becomes bothersome and barely tolerable, then the study drug dosage is reduced to the last dose tolerated without stopping treatment. If the side effect is intolerable, then the study drug is discontinued for one week and then restarted at the lower dosage that was previously tolerated.

If side effects occur that may be more serious, such as heart palpitations, skin rash, anxiety, confusional states, panic, then the patient will be evaluated. For heart palpitations, an ECG will be

obtained. Investigators can initially attempt dose reduction to the previous well tolerated dose instead of treatment interruption. If patients developed serious or intolerable side effects requiring cessation of study drug, the drug will be stopped for one week. If the side effects disappear, a second attempt will be made to reintroduce the study drug after one week at the previous lower dose that the participant tolerated better. If the dose is well tolerated, the patient will be continued at this dose for the remainder of the study without further dose escalation. If the study medication is stopped, the patient will no longer receive the study drug, but will be followed in the study according to the protocol, in keeping with the "intention-to treat" paradigm.

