#### **Safety concerns related to nortriptyline:**

Study participants will receive nortriptyline or placebo. Nortriptyline is a tricyclic antidepressant (TCA). Tricyclic antidepressants act to inhibit the reuptake of the neurotransmitters norepinephrine and serotonin, leading to an increase in their effects. Contraindications to nortriptyline include: a) hypersensitivity or allergy to any tricyclic antidepressant drug, b) concomitant therapy with a monoamine oxidase inhibitor, c) recent myocardial infarction, and d) glaucoma. The dose (10-75 mg) of nortriptyline in this study is on the lower end of the conventional antidepressant dose (50-150 mg) approved to treat depression. Patients with cardiovascular disease should be given nortriptyline only under close supervision due to increased risk of myocardial infarction, arrhythmia and stroke. Arrhythmias may develop especially in patients with hyperthyroidism or those receiving thyroid hormone replacement medication. Patients with a history of seizures will be excluded from the study because nortriptyline is known to lower the convulsive threshold. Concurrent administration of cimetidine with nortriptyline can produce

clinically significant increases in the plasma concentrations of nortriptyline.

Study participants will have an electrocardiogram (ECG) during screening and at follow-up visits 9 and 12 weeks after randomization to monitor for any signs of study-drug related toxicity. In addition, a complete blood count (CBC), a metabolic panel including sodium, potassium, chloride, carbon dioxide, calcium, magnesium, blood urea nitrogen (BUN), creatinine, and a hepatic panel including albumin, total protein, alkaline phosphatase, alkaline aminotransferase (ALT), aspartate aminotransferase (AST), and bilirubin will be performed at the week 12 visit. The following treatment interruption or termination rules will be followed:

- If hypokalemia (potassium  $<3.5$  mEq/L) or hypomagnesia (magnesium  $<1.5$  mEq/L) is present at the week 12 visit, study participants will be given oral supplementation and electrolyte measures will be repeated within a week. If the electrolyte imbalance has not been remedied with oral supplementation as indicated by a serum potassium of  $<3.0$  mEq/L and serum magnesium of less than 1.0 mEq/L, the study drug will be interrupted or terminated with tapering, as needed. The participant will continue with 15 week and 18 week follow-up visits as scheduled.

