- If significant elevations ( $>2$  times upper limit or normal) occur in alkaline phosphatase, alkaline aminotransferase (ALT), or aspartate aminotransferase (AST) at the week 12 visit, these enzymes will be repeated within a week. If any of these enzyme elevations persist above 3 times the upper limit of normal, the study drug will be interrupted or terminated with tapering, as needed. The participant will continue with 15 week and 18 week follow-up visits as scheduled.
- If thrombocytopenia ( $<100,000$  cells per  $\mu$ L) is present at the week 12 visit, the study drug will be interrupted or terminated with tapering, as needed. The participant will continue with 15 week and 18 week follow-up visits as scheduled.

In general, side effects to nortriptyline are fewer than other TCAs since it does not have significant anticholinergic effects, however, side effects can still occur and can include: drowsiness, sedation, fatigue, dizziness, seizures, palpitations, blurred vision, dry mouth, constipation, and skin rash. A standardized management plan for the most common side effects as well as the more serious side effects are outlined below:

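### The electrolyte rule starts on low potassium or low magnesium, but its stop condition, read literally, needs both to be severely low

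*Protocol*

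**What the plan says.** Three places in the protocol set the rule.

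- **Trigger (section 5.7, safety concerns related to nortriptyline).** At week 12, potassium below 3.5 mEq/L "or hypomagnesia (magnesium" below 1.5 mEq/L) leads to oral supplementation and a repeat measurement within a week. One low value is enough.
- **Stop condition (same bullet).** For an imbalance that persists, the potassium limit is 3.0, and the sentence goes on: "mEq/L and serum magnesium of less than 1.0 mEq/L, the study drug will be interrupted or terminated with tapering, as needed". The two severe cut-offs are joined by *and*.
- **Stop and unmask (section 5.12).** This opens by citing the same rule, "As described in Section 5.7, if the electrolyte imbalance has not been remedied with oral supplementation", and then sets the same joint test of both cut-offs, "as indicated by a serum potassium of <3.0 mEq/L and serum magnesium of less than 1.0 mEq/L". When that test is met, the drug is stopped and the patient, primary care provider and investigator are unmasked.

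The next bullet of section 5.7, on liver enzymes, works differently. It acts "If any of these enzyme elevations persist above 3 times the upper limit of normal", so one enzyme is enough. The document history (section 9.5) has the same *and* where the electrolyte text was added, so the word is not an artefact of text extraction.

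**The concern.** A patient can enter the rule on one electrolyte but, on the words, can meet the stop condition only on both. A patient who enters with low potassium and keeps a normal magnesium cannot meet it however low the potassium stays, and the same holds the other way round. This is a stated safety threshold for a drug whose risks, as listed in section 5.7, include arrhythmia and QTc prolongation.

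Two things are at stake. A patient with one severely low electrolyte could be kept on the drug for the rest of the scheduled treatment and taper. And the seven centers could handle the same result differently: one stops and unmasks, another continues masked at full dose, and both can say they followed the protocol.

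**Working it through.** No sample size, power or error-rate figure is involved, and the plan states no figure to reproduce. The check is a truth table and a dose count.

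**Logic of the rule**

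Write K for potassium and Mg for magnesium, in mEq/L.

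- Trigger (5.7): K < 3.5 or Mg < 1.5
- Stop as written (5.7 and 5.12): K < 3.0 and Mg < 1.0
- Stop with the change: K < 3.0 or Mg < 1.0

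| Retest result | Stop as written | Stop with *or* |
|---|---|---|
| K < 3.0, Mg < 1.0 | yes | yes |
| K < 3.0, Mg ≥ 1.0 (e.g. 2.5 and 1.8) | no | yes |
| K ≥ 3.0, Mg < 1.0 (e.g. 4.0 and 0.8) | no | yes |
| K ≥ 3.0, Mg ≥ 1.0 | no | no |

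The two wordings differ exactly in the two rows where a single electrolyte is severely low. The example values are illustrations, not trial data.

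**Window**

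After screening, the data collection schedule (appendix 9.2) has the metabolic panel only at week 12. A retest within a week falls at week 13 at the latest. Section 3.3 ends dosing at week 17. The rule therefore governs about weeks 13 to 17.

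**Dose in that window, for a nortriptyline patient at full dose (section 3.3)**

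- As scheduled: 75 mg for 14 nights, 50 mg for 7, 25 mg for 7. That is 75 × 14 + 50 × 7 + 25 × 7 = 1050 + 350 + 175 = 1575 mg.
- Taper begun at week 13 in the same steps (assumption): 50 × 7 + 25 × 7 + 0 × 14 = 350 + 175 = 525 mg. Avoided: 1575 − 525 = 1050 mg.
- Immediate stop at week 13: 0 mg. Avoided: up to 1575 mg. The wording allows this, since 5.7 permits interruption and 5.12 speaks of stopping.

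These are amounts of drug, not measures of risk. They apply only to patients on nortriptyline who reached 75 mg.

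**Other provisions that could act in that window**

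| Provision | What sets it off |
|---|---|
| Week-12 ECG, at the same visit as the blood draw (5.4), with the stop for QTc prolongation or dysrhythmia (5.7) | an ECG finding |
| Palpitation rule (5.7) | a symptom, then an ECG |
| One-week stop (3.4): "If patients developed serious or intolerable side effects requiring cessation of study drug, the drug will be stopped for one week" | a side effect |
| Week-15 visit (5.4): history, vital signs, review of laboratory results | a scheduled contact; no stop threshold given |
| Unmasking for significant arrhythmia (5.12) | an arrhythmia |
| Discretionary unmasking (5.12): "In unforeseen situations where the clinical center principal investigator considers unmasking is in the best interest" | the investigator's judgement, in unforeseen situations |

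None of these sets a stop threshold on an electrolyte value. Scheduled ECGs end at week 12: "Study participants will have an electrocardiogram (ECG) during screening and at follow-up visits 9 and 12 weeks after randomization". No chemistry panel is scheduled at week 15 or 18.

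**The case against.** The strongest reply is that the literal reading is the less natural one. The sentence asks whether the imbalance just found and treated has been remedied, so the two cut-offs can be read as the reference value for each electrolyte. On the literal reading, a patient treated for low potassium would be stopped only after also developing a severe magnesium deficit, which is a different problem. This stands as an account of what was probably meant. It does not settle the text: neither section says either or respectively, and the same bullet uses *or* for its trigger, so a careful reader at a center could take the change to *and* as deliberate.

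The second reply is that the patient is better protected than the rule alone suggests. The ECG is done at the visit where the electrolytes are drawn and carries its own stop, the week-15 visit includes a laboratory review, and investigators may reduce or interrupt the drug for side effects. This also stands, and it keeps the point small. But those stops need an ECG finding, a symptom or a judgement. Discretionary unmasking is reserved for unforeseen situations, and low potassium is a foreseen one with its own rule.

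A reader might infer that the protocol obliges centers to continue dosing in isolated severe hypokalaemia. It does not. The rule sets a point at which the drug must be stopped or interrupted, and nothing in it forbids stopping earlier.

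**Conclusion.** The stop condition in 5.7 and 5.12 is wrong as written, because it does not match its own trigger and leaves out severe depletion of one electrolyte alone. It is a minor correction to a safety threshold. The frequency cannot be estimated from the protocol, the window is about weeks 13 to 17, and the drug avoided per full-dose nortriptyline patient runs from 1050 mg (assuming the one-capsule-a-week taper starts at week 13) to 1575 mg (immediate stop).

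Two stronger conclusions might be drawn, and the protocol supports neither. One is that the gain could never exceed a taper begun two weeks early; the interruption and stop wording allows more. The other is that the fault threatens the trial's statistical conclusions; power and alpha do not depend on it. The only link to the efficacy data is that any patient unmasked under this rule before week 15 would give the week-15 GCSI unmasked, and that visit can form part of a qualifying pair for the primary outcome. The same would follow if sites already apply the cut-offs separately.

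**What to change.** In section 5.7, state the stop condition as serum potassium <3.0 mEq/L or serum magnesium <1.0 mEq/L. Make the same change in section 5.12, which cites 5.7, and send sites a short note.

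The cost is one word in each of two sections. The downside is possibly a few more late drug stops and unmaskings, with the week-15 GCSI of those patients then collected unmasked. Follow-up visits continue after a stop in any case, as 5.12 already provides. Whether a persistent electrolyte deficit should unmask at all is a separate decision that this correction does not require.
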